## List of Abbreviations

- \*AE: Adverse event
- \*aGVHD: Acute Graft Versus Host Disease
- \*Allo-SCT: Allogeneic stem cell transplant
- \*BTK: Bruton's tyrosine kinase
- \*cGVHD: Chronic Graft versus Host Disease
- \*CLL: Chronic lymphocytic leukemia
- \*CTCAE: Common terminology criteria for adverse events
- \*DSMAC: Data Safety Monitoring and Accrual Committee
- \*EMR: Electronic medical record
- \*GVHD: Graft Versus Host Disease
- \*ITK: IL-2 inducible T cell kinase
- \*NHL: Non-Hodgkin's lymphoma
- \*SAE: Serious adverse event

## Study Summary

Title	Combination Ibrutinib and Rituximab for Treatment of Chronic Graft-Versus-Host Disease Following Allogeneic Stem Cell Transplant
Short Title	Ibrutinib and Rituximab for Steroid-Refractory or Dependent Chronic GVHD
Protocol Number	D17120
Phase	Phase 1/2
Methodology	Open label, Within-Subject Dose-Escalation Study
Study Duration	2 years (patients will be followed after 6 months for survival only)
Study Center(s)	Single center
Objectives	To determine the safety and efficacy of Ibrutinib and Rituximab combination therapy for steroid-refractory or -dependent chronic GVHD following allogeneic stem cell transplant.
Number of Subjects	15
Diagnosis and Main Inclusion Criteria	Steroid refractory or dependent chronic graft-versus-host disease (diagnosis to be based on histologic sampling and/or via clinical criteria; see Attachments) > 18 years old Karnofsky Performance Status 60 or greater

Study Product, Dose, Route, Regimen	
Within-Subject Dose-Escalation Format:
 
 
-The first 5 subjects will receive treatment as follows: 
 
-Ibrutinib 140 mg po once daily
 
-Rituximab 375 mg/m^2 IV weekly x4
 
 
 
-Adverse events will be defined as per the NCI Common Terminology Criteria for Adverse Events (CTCAE) 
 
-if no adverse events <math>\geq</math> non-hematologic grade 3 or <math>\geq</math> hematologic grade 4 are noted after 1 week at 140 mg daily, the Ibrutinib dose schedule will be increased to 280 mg daily
 
-if no adverse events <math>\geq</math> non-hematologic grade 3 or <math>\geq</math> to hematologic grade 4 are noted after 1 week at 280 mg daily, the Ibrutinib dose schedule will be increased to 420 mg daily
 
- the potential exists for a 2nd weekly x4 Rituximab course 8 weeks after initial Rituximab therapy, if no response or an incomplete response is noted
 
 
 
 
Expansion cohort:
 
 
- following accrual of the 5 initial subjects, an additional 10 subjects will be accrued, with dosing to be informed by the results of the within-subject dose escalation cohort
 

Duration of administration	
Ibrutinib: ongoing (indefinite), with re-assessment of patient tolerance and response at 6 weeks, 3 months and 6 months
 
Rituximab: weekly x4, with or without a repeat 8 weeks after the initial therapy, depending on the patient's initial clinical response

Reference therapy	
Patients may have received steroids or other alternative GVHD regimens (with no new therapy for at least two weeks prior to the start of this protocol), without benefit,
 
OR
 
Patients may have shown an initial steroid benefit, but demonstrate an inability to undergo steroid taper due to persistent GVHD upon attempted steroid dose reduction.

Statistical Methodology	
GVHD response rates at 6 weeks, 3 months and 6 months will be assessed using exact binomial methods combining the initial dose escalation and expansion cohorts.
 
Univariate and multivariate analyses will be used to identify independent correlates of both safety and efficacy.

-------------------------	--------------------------------------------------------------------------------------------------------------------------------------------------------------------------------------------------------------------------------------------------------------------------------------------------

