## 7 Statistical Plan

## 7.1 Statistical Methods

GVHD response rates based on the GVHD Global Severity Score and Clinical Assessment ( Attachment 1) at 6 weeks, 3 months and 6 months will be assessed using exact binomial methods combining the initial dose escalation and expansion cohorts. With the expansion cohort after the safety dose escalation phase, a total of 15 patients will be available for evaluation. An exact test for proportions with a null hypothesis of a 15% response rate, an alternative hypothesis of a 50% response rate, and a one-sided significance level of 0.10, would have a power of 85% using 15 subjects, including a Bonferroni correction for looking at the 6 week, 3 month and 6 month response rates. This test rejects the null hypothesis if 6 out of 15 subjects respond. If only the 10 subjects from the expansion cohort are used, the null is rejected if 4 out of 10 respond, and the power is reduced to 0.83. Calculations were done in the PASS 2008 package.

Two-sample t-tests for continuous data and Fisher's exact test for binary data will be used to compare responders and non-responders for the purpose of identifying independent *biomarker* correlates of treatment response. The power and precision of these comparisons will depend on the number of responders and non-responders compared.

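### Section 7.1's one-marker tests cannot identify independent correlates, and the Summary's multivariate and safety-correlate analyses are absent from the plan

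*Combined protocol and SAP*

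**What the plan says.** The Statistical Methodology row of the Study Summary states: "Univariate and multivariate analyses will be used to identify independent correlates of both safety and efficacy". It names no model, no covariates and no outcome variable for safety.

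Section 7.1 is the only other place where a correlate analysis is described. The method is: "Two-sample t-tests for continuous data and Fisher's exact test for binary data will be used to compare responders and non-responders". The stated aim is "for the purpose of identifying independent *biomarker* correlates of treatment response". One caveat follows: "The power and precision of these comparisons will depend on the number of responders and non-responders compared". No multivariable model, covariate list or selection rule appears, and nothing compares subjects with and without toxicity.

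On scale, 7.1 says that "a total of 15 patients will be available for evaluation". Section 3.3 lists ten markers (sIL2Ra, CX3CL1, CXCL9, CXCL10, CCL22, CCL4, ST2, CD146, CCR5, FOXP3), each measured before treatment and at six weeks, three months and six months. Section 2 makes laboratory correlates of response the second secondary objective, and Section 3.3 makes them the second secondary endpoint.

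**The concern.** There are three mismatches. The Summary promises a multivariate analysis that the statistical section does not contain. It promises correlates of safety, which is the subject of the primary objective, and 7.1 looks only at response. And 7.1 attaches the word independent to tests that adjust for nothing.

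The third matters most, because it survives even if 7.1 is taken to govern. An analyst who follows 7.1 exactly would report markers as independent correlates on evidence that shows only marginal association. An analyst who follows the Summary would have to invent a model after seeing the data, in a sample too small for it to carry that conclusion. Either way, a stated secondary objective ends in a claim that the analysis does not support.

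**Working it through.** **1. The two statements side by side**

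| Element | Study Summary | Section 7.1 |
|---|---|---|
| Univariate analysis | Yes | Yes: t-test, Fisher's exact test |
| Multivariate analysis | Yes | None |
| Correlates of efficacy | Yes | Yes, biomarkers only |
| Correlates of safety | Yes | None |
| Claim of independence | Yes | Yes |

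**2. The plan's own figure.** The only power calculation in 7.1 is for the response rate: 15% against 50%, one-sided 0.10 with Bonferroni over three time points, rejecting at 6 or more of 15.
- P(X ≥ 6 | n = 15, p = 0.50) = 0.849; the plan states 85%.
- P(X ≥ 6 | n = 15, p = 0.15) = 0.0168, below 0.10/3 = 0.0333.

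The figure reproduces, but it says nothing about the correlate analysis, for which no calculation is given.

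**3. What a one-marker test can show.** Suppose marker A differs by δ standard deviations between responders and non-responders. Suppose marker B has within-group correlation ρ with A and no relation to response once A is known. The expected difference in B is then ρ × δ, which is not zero unless ρ is zero. A t-test on B can rightly detect that difference, yet B is not an independent correlate. The same holds for Fisher's test on binary markers. Section 1.1 reports that six of the listed markers fell in responders to ibrutinib in one patient series, so markers that move together are a realistic prospect. The correlations themselves are not given.

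**4. Subjects available for a joint model.** The smaller outcome class is min(R, 15 − R), where R is the number of responders, so it is at most 7.
- Two terms: 7/2 = 3.5 subjects per term at best.
- Ten terms: 7/10 = 0.7 at best.

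The expected size of the smaller class is Σ min(k, 15 − k) × P(R = k):

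| Response rate | Source | Expected smaller class | Per term, 2 terms | Per term, 10 terms |
|---|---|---|---|---|
| 50% | 7.1, alternative | 5.93 | 2.96 | 0.59 |
| 67% | 1.1, ibrutinib alone | 4.79 | 2.39 | 0.48 |
| 15% | 7.1, null | 2.25 | 1.12 | 0.22 |

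These are upper figures. Section 7.2 counts subjects as evaluable for efficacy if they stay at least six weeks and does not replace toxicity withdrawals, so fewer than 15 may be evaluable.

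**5. Complete separation in a logistic model.** The assumptions are mine: 7 responders and 8 non-responders, and independent normal markers unrelated to response. The simulated share of data sets in which the markers split the groups perfectly, so that no finite maximum-likelihood estimate exists, is:

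| Markers in model | Separation |
|---|---|
| 2 | under 1% |
| 3 | about 2% |
| 5 | about 16% |
| 7 | about 52% |
| 10 | about 96% |

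As a cross-check, if all 15 labels are random, the probability is 2⁻¹⁴ × Σ C(14, k) for k = 0 to d, with d markers. This gives 0.21, 0.60 and 0.97 for d = 5, 7 and 10. It is higher at 5 and 7 because it averages over unbalanced splits as well; at 10 the two agree.

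**The case against.** **No passage puts all ten markers into one model.** This stands. The Summary sentence does not mention biomarkers, and its covariates could be clinical. The count of ten is also open: Section 1.1 describes CD146 and CCR5 as expressed together on one T-cell subset, so they might be a single variable. The ten-marker figures are an assumed worst case, not a description of the plan.

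**Small models can be fitted.** This stands too. A reader might infer that 15 subjects rule out any multivariable model. The separation rates for two and three markers do not support that. What they leave is a weaker and sufficient point: at 3.5 or fewer subjects per term, such a model would not credibly establish independence.

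**Section 7.1 already carries a caveat, and if it governs, no model is fitted.** If 7.1 governs, the risk of unstable coefficients does fall away. But the caveat concerns power and precision. It does not turn an unadjusted comparison into evidence of independence, and it does not account for the missing multivariate and safety-correlate analyses.

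**The correlates are exploratory in spirit.** No hypothesis, significance level or decision rule is attached to them, and Section 2 speaks only of relevant correlates. That limits the consequences. But the documents do not label the work exploratory, and they list it as a secondary objective and endpoint. Beside the word multivariate, independent reads in its statistical sense.

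**Conclusion.** The point holds. The Summary and 7.1 disagree on whether a multivariate analysis and an analysis of safety correlates exist, and 7.1 claims independence for tests that cannot show it. That part rests on the text alone.

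A model added later would not repair the claim. The ceiling of 7 in the smaller class follows from the sample of 15 and holds at any response rate. The separation figures, from under 1% with two markers to about 96% with ten, depend on the assumed 7/8 split and independent noise markers.

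A reader might also infer that the biomarker claim must be false, or that the trial's main conclusions are affected. Neither follows. A marker may truly be an independent correlate; this plan cannot establish it. The primary safety endpoint and the response-rate test do not depend on the correlate analysis. The wording should be corrected, but this does not undermine the design.

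**What to change.** - In the Summary sentence, delete multivariate and independent. In 7.1, delete independent.
- In both places, state that univariable associations between biomarkers and response will be described with estimates and confidence intervals, and that they are unadjusted and exploratory.
- Delete safety from the Summary sentence, or add the matching univariable comparison for safety to 7.1.

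While the sentence is being edited, it would help to say which marker time point is compared with which response assessment, since 7.1 does not.

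The change is wording in two places. It needs no further patients, samples or visits. The downside is a more modest claim about the biomarkers.

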# 1 Introduction

This document is a protocol for a human research study. This study is to be conducted according to US and international standards of Good Clinical Practice (FDA Title 21 part 312 and International Conference on Harmonization guidelines), applicable government regulations and Institutional research policies and procedures.

## 1.1 Background

Allogeneic stem cell transplant (allo-SCT) remains a potentially curative treatment modality for a variety of hematologic malignancies. Development of graft-versus-host disease (GVHD) following transplant poses clinical challenges and contributes significantly to post-transplant morbidity and mortality (1,2,3). GVHD is an immunologic condition caused by a reaction of donor T lymphocytes against host tissues after allogeneic transplant. The pathophysiology of GVHD is dependent on the presence of T-cells in the donor graft, allo-antigenicity between donor and recipient and an immunologically incompetent host. GVHD can manifest as either acute disease, generally affecting the skin, GI tract and liver, or chronic, with the latter being the primary cause of late morbidity and mortality following allo-SCT (1,2). Traditional distinctions between acute and chronic GVHD, based on time of onset following transplant, have largely given way to qualitative clinical differences, as the temporal onset has varied in the era of non-ablative allo-SCT and the National Institutes of Health (NIH) consensus development project has better defined diagnostic and staging criteria for chronic GVHD (2).

Acute GVHD (aGVHD) is known to be mediated almost exclusively by donor T cells, whereas the pathophysiology of chronic GVHD (cGVHD) is less well defined, though both CD4+ T-cells and B cells have been implicated. Thus, treatment of cGVHD remains challenging, with only 30-50% of patients responding to first-line (steroid) therapy. Those patients who develop steroid-refractory disease carry a poor prognosis, owing to the lack of any clear consensus on second-line therapy. Even those who initially respond to steroid therapy warrant second-line intervention to minimize the significant morbidity and mortality risks of longstanding steroid use (1,2,3). Since donor B cells have been shown to play an increasing role in the pathophysiology of cGVHD, the prospect of B-cell depletion has been raised as an effective modality for chronic GVHD management (4). Cutler et al. demonstrated the benefit of rituximab in the treatment of steroid-refractory cGVHD (5), and follow-up studies have confirmed the prophylactic efficacy of this agent in minimizing development of steroid-requiring cGVHD (6,7). Notably, although the overall clinical response rate of established cGVHD to rituximab was high (70%), complete responses were rare, emphasizing the need for additional agents in this area (5).

In light of data indicating a role of Th2 cells in the development of cGVHD (8), studies have suggested the potential utility of ibrutinib in cGVHD treatment (9). Ibrutinib is an irreversible inhibitor of Bruton's tyrosine kinase (BTK) and IL-2 inducible T cell kinase (ITK) that targets Th2 cells and B cells (9). It has been used as mono- or combination therapy in various hematologic malignancies (10,11), including mantle cell lymphoma (MCL;12) and chronic lymphocytic leukemia (CLL;13). Various murine studies have supported ibrutinib as a potential agent to treat GVHD, including demonstration of efficacy in two complementary murine models (14). One involved T-cell driven sclerodermatous cGVHD and another demonstrated allo-antibody driven multi-organ system cGVHD, with manifestation of bronchiolitis obliterans chronic pulmonary GVHD. These data suggest a promising therapeutic role for ibrutinib in the management of (B-/T-cell driven) cGVHD, and this has been borne out by human studies, including a multi-center, open-label, phase II trial showing efficacy in steroid-refractory GVHD (15). This study, consisting of 42 patients with cGVHD who had failed 1-3 prior therapies, demonstrated an overall response rate (ORR) of 67%, with over 70% sustained responses (at least 20 weeks), leading to ibrutinib having recently been granted FDA approval for the treatment of cGVHD after failure of at least one line of systemic therapy.

While identification of uniquely correlative plasma biomarkers in the cGVHD setting remains incomplete, two potential biomarkers of interest include suppression of tumorigenicity 2 (ST2) (16) and CD4CD25FOXP3 Tregs (17), with potential relevance of these to both cGVHD development and therapeutic response. In addition, an activated Th17-prone T-cell subset expressing both CD146 and CCR5 has been shown to play a role in cGVHD, with potential sensitivity to pharmacologic inhibition (18, 19). Further, in a subset of 42 patients with cGVHD receiving ibrutinib following resistance to prior intervention, those responding were found to manifest decreased levels of sIL-2Ra, CX3CL1, CXCL9, CXCL10, CCL22 and CCL4 (18, 20).

Another development on the clinical front has been the use of combination ibrutinib/rituximab therapy for patients with CLL, shown to be a well-tolerated, effective regimen, with minimal toxicity (21). To that end, we recently

## **1.2 Pharmaceutical agent data from clinical pharmacology**

### **Rituximab**

Rituximab is a genetically engineered chimeric murine/human monoclonal antibody, directed against the CD20 antigen expressed on B-lymphocytes. It has IgG-1 kappa immunoglobulin containing murine light- and heavy-chain variable regions and human constant regions. Rituximab is routinely used for B-cell non-Hodgkin's lymphoma (NHL) and other CD20 expressing B-cell hematologic malignancies and is FDA approved for diffuse large B-cell, CD20 positive NHL in combination with CHOP or other lymphoma-specific cytotoxic chemotherapy regimens. It is also FDA approved in combination with cyclophosphamide, vincristine, and prednisone (CVP) chemotherapy as first-line treatment for untreated CD20 positive follicular non-Hodgkin's lymphoma, as well as in combination with fludarabine and cyclophosphamide for CD20 positive chronic lymphocytic leukemia (CLL). Rituximab is FDA approved as single-agent maintenance therapy for patients with CD20 positive follicular NHL.

### **Ibrutinib**

Ibrutinib is a potent and irreversible Bruton's tyrosine kinase (BTK) inhibitor (9). BTK is responsible for the proliferation, differentiation, apoptosis, and cell migration of B cells (9). A Phase II study showed benefit for relapsed or refractory mantle cell lymphoma (MCL) in median progression-free survival (PFS) and median overall survival (OS). (12) A Phase III trial (MCL3001) demonstrated benefit in PFS with single-agent ibrutinib as compared with single-agent temsirolimus for patients who had received at least one prior rituximab-containing regimen for relapsed or refractory MCL (22) Another Phase III trial, RESONATE, showed significantly improved response rate (RR), PFS and OS with ibrutinib versus ofatumumab for patients with CLL or small lymphocytic lymphoma (SLL). (23) In addition, results of the Phase III RESONATE-2 trial showed that ibrutinib was superior to chlorambucil as assessed by RR, PFS, OS and improved hematologic variables for patients with previously untreated CLL or SLL (24).

## **1.3 Preclinical Data**

Available data on ibrutinib as an irreversible inhibitor of BTK and IL-2 inducible kinase targeting Th2 cells and B cells (30).

Murine study data support prophylactic benefit of ibrutinib in chronic GVHD (25).

## **1.5 Dose Rationale and Risk/Benefits**

There are multiple studies supporting the tolerability and efficacy of rituximab in patients with cGVHD after allogeneic stem cell transplant, primarily patients with sclerodermatous and/or lichenoid cutaneous disease (3). Several prospective studies have used rituximab 375 mg/m^2 weekly x4, with the option for a second course at 8 weeks following initial therapy, based on the adequacy of response. There are also phase 1b/2 data supporting 420 mg daily as a safe and effective dose schedule for ibrutinib in post-transplant human cGVHD (15).

A single-arm phase II study assessing the safety and activity of ibrutinib and rituximab for patients with high risk CLL supports the tolerability of this combination at respective dose schedules of 420 mg daily (indefinite) and 375 mg/m^2 weekly x4, then monthly x5, with the total duration of rituximab being 6 months. However, since those patients were not allogeneic stem cell transplant recipients, a within-subject dose-escalation format will be utilized in this current study to optimize risk assessment in the post-transplant setting (see Study Summary, pages 1-2).

## 2 Study Objectives

Primary objective: to assess the safety and tolerability of ibrutinib/rituximab combined therapy in patients with steroid dependent or refractory GVHD.

Secondary Objectives: 1) to assess the clinical efficacy of ibrutinib/rituximab combined therapy in patients with steroid dependent or refractory GVHD.

2) To determine relevant laboratory correlates underlying clinical response, or lack thereof.

## 3 Study Design

### 3.1 General Design

This is a non-randomized, open label, within-subject study to assess safety and preliminary efficacy for combination ibrutinib and rituximab in an allogeneic stem cell transplant recipient population, using a within-subject dose-escalation format.

Duration: 6 months, depending on response to therapy and ongoing clinical status.

### 3.2 Primary Study Endpoints

1. Safety of combination Ibrutinib and Rituximab therapy for steroid refractory or dependent chronic GVHD, based on review of dose-limiting toxicities and results of the within-subject dose-escalation format.

### 3.3 Secondary Study Endpoints

1. Response rate of clinically significant GVHD based on NIH criteria (from 2014 NIH Consensus Development Project, see Attachment 1) at the following time points: six weeks, three months, and six months after initiation of therapy.
2. Laboratory correlates: The following serum biomarkers will be checked at the specified time points: pre-treatment; six weeks; three months; six months.

Elisa/Luminex	Flow Cytometry
sIL2Ra	CD146
CX3CLI	CCR5
CXCL9	
CXCL10	
CCL22	
CCL4	
ST2	FOXP3

## 4 Subject Selection and Withdrawal

### 4.1 Inclusion Criteria

Patients fulfilling the following criteria will be eligible for registration onto this study:

1. Men and women  $\geq 18$  years old who are recipients of an allogeneic bone marrow, cord blood or peripheral blood stem cell transplant.  
(There will be no restrictions based upon underlying disease, donor source, degree of HLA match, intensity of pre-transplant conditioning regimen or use of prior donor lymphocyte infusion(s).)
2. Chronic GVHD that is confirmed by clinical assessment and/or biopsy.
3. Either steroid-refractory or steroid-dependent cGVHD.
4. Karnofsky performance status  $\geq 60$ .

